10.3.1. Summary of Treatment-emergent Adverse Events

An overall summary of TEAEs table will be presented, and it will include the following events:

- Any TEAEs
- Treatment-emergent serious adverse events (TESAEs)
- TEAEs leading to study drug discontinuation
- TEAEs related to study drug (ie, treatment related TEAEs)

- TEAEs related to study drug and leading to study drug discontinuation
- TESAEs leading to study drug discontinuation
- TESAEs related to study drug (ie, treatment related TESAE)
- TESAEs related to study drug and leading to study drug discontinuation
- Deaths

In addition, summary tables will be presented for each of the individual events listed above. The number and percentage of subjects who experienced TEAEs will be presented by SOC and by PT within SOC, and separately by PT only. The SOCs will be sorted alphabetically, and the PTs will be sorted by descending frequency within the SOCs based on the total column. A subject will be counted only once within the same SOC and within the same PT.

The cumulative number and percentage of subjects with TEAEs will be summarized by intensity (mild, moderate, severe), and by relationship to study drug ('related' versus 'not related'). If a subject experienced more than 1 TEAE within different intensity or relationship categories within the same SOC/PT, only the worst case (worst intensity and related TEAE) will be reported.

All AEs (including TEAEs and non-TEAEs) will be provided in a listing that will include the subject identifier, SOC, PT, and the reported term, date of onset and study day, date of resolution and study day, the seriousness, the intensity, the relationship to each individual study drug (for TEAEs), duration, the action taken, and the outcome. All TEAEs will be flagged in the listing.

Separate listings will also be generated for deaths, serious adverse events (SAEs), and discontinuations due to TEAEs.

10.3.2. TEAEs Reported as Infusion-associated Reaction

For any AE, the reporting investigator is requested to enter onto the AE eCRF whether the AE is deemed to be an IAR and determine its relationship to each of the study drug components (ATB200 and AT2221).

To further characterize TEAEs considered by the reporting investigators to be IARs, a summary table of TEAEs reported as IARs will be provided. The number and percentage of subjects who experienced IARs will be presented by SOC and by PT within SOC. A subject will be counted only once within the same SOC and within the same PT.

A summary of IARs will also be presented for relationship to each treatment component (ATB200 and AT2221) as well as for the co-administration. Additional summary outputs (tables and/or plots) will be provided to describe the clinical characteristics of the IARs by treatment group, including the event rates, changes in intensity over time, and time to first IAR (as described in Section 10.3.3.2). The IAR summary will also be presented by prior history of IARs (yes/no).

A listing that includes treatment-emergent IARs, serious IARs, IAR-related deaths, and IARs leading to study drug discontinuation will be provided. In addition, a listing displaying the number of infusions and infusions that were associated with IARs by each individual subject who had an IAR, will be provided. For each subject, this listing includes subject ID, whether or not pre-medication was given, number of infusions received, number of infusions that were

associated with IARs, percentage of infusions associated with IARs, and a sequential/horizontal listing of the number of IARs corresponding to (or associated with) each infusion.

A summary of the number of subjects with TEAEs that are IARs (ie, IAR-TEAEs), the total number of IARs, and the number of subjects with 1, 2, 3 to 4, or ≥ 5 IARs will be presented.

To characterize the overall number of infusions associated with IARs during the study, the following will be summarized:

- For all subjects (regardless of whether they experienced an IAR), the overall total number of infusions administered during the study, and the number and percentage of infusions administered that were associated with IARs;
- For subjects who experienced IARs, the total number of infusions administered, and the number (and percentage) of infusions administered that were associated with IARs.

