Subjects in Cohort 1 will participate in Screening, Baseline, Stage 1 (3-period, fixed-sequence, single-ascending dose of ATB200 alone), Stage 2 (2-period, fixed-sequence, multiple-dose of 20 mg/kg ATB200 co-administered with multiple-ascending doses of AT2221), and Stage 3 (a 24-month extension stage with continued dosing of 20 mg/kg ATB200 co-administered with 260 mg AT2221) of the study. Stage 4 treatment period will begin at the end of Stage 3 and continue as an open-label extension until subject withdrawal, regulatory approval or marketing authorization and/or commercialization in the participating subject's country, or study termination by Amicus.

Subjects in Cohorts 2, 3, and 4 will participate in Screening and Baseline for Stage 3 of the study, as well as Stage 3 dosing-visits. Additionally, subjects in Cohort 3 will participate in serial 24-hour PK visits. Subjects in Cohort 2 and 4 will not participate in PK analyses. The procedures and assessments performed are as follows:

Screening:

- At Screening for either Stage 1 or Stage 3, all subjects will provide informed consent and undergo review of eligibility criteria. Assessments for all subjects include medical history (including forced vital capacity [FVC] and 6MWT, CK, alanine aminotransferase [ALT], aspartate aminotransferase [AST], and urine Hex4 lab results) and history of falls; review of prior and concomitant medications and nondrug therapies; vital signs (heart rate [HR], respiration rate [RR], blood pressure [BP], and temperature); height; weight; comprehensive physical examination (PE); 12-lead electrocardiogram (ECG); clinical safety laboratory assessments (serum chemistry, hematology, and urinalysis); urine pregnancy test; and urine sample for Hex4. Blood samples will also be obtained for immunological assessments (total and neutralizing antibodies, exploratory pro-inflammatory cytokines/other biomarkers of immune system activation, cross-reactivity to alglucosidase alfa, and immunoglobulin E [IgE]), exploratory biomarkers of Pompe disease, and immunogenicity. For subjects in Cohorts 1, 2, and 4, a history of prior infusion-associated reactions (IARs) will also be obtained, and gene that encodes human acid α -glucosidase (*GAA*) genotyping will be performed for those who are unable to provide *GAA* genotyping report at screening. A subject who meets all of the inclusion criteria and none of the exclusion criteria will be assigned to Stage 1 as described above in [Table 1](#).

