Baseline:

- Baseline assessments for all subjects include review of eligibility criteria; medical history and history of falls, adverse event (AE) and serious AE (SAE) inquiry, review of prior and concomitant medications and nondrug therapies; vital signs (HR, RR, BP, and temperature); weight; brief PE; ECG; Rasch-built Pompe-specific activity (R-PAct) Scale; Rotterdam Handicap Scale (RHS); Fatigue Severity Scale (FSS); Patient-reported Outcomes Measurement Information System (PROMIS[®]) for dyspnea, fatigue, physical functioning, and upper extremity; pulmonary function tests (PFTs); motor function tests; and

muscle strength tests for all subjects. Additionally, a history of IARs will be obtained for subjects in Cohorts 1, 2, and 4.

- Retrospective data for patients from Cohorts 1, 2, and 3: All available data for 6MWT, pulmonary function tests, other motor function tests such as 10-meter walk, 4-stair climb, and Gower's, quantitative (dynamometry) and qualitative muscle strength tests, Gait, Stairs, Gower, and Chair maneuver (GSGC) score, and patient-reported outcomes (PROs), if available should be recorded in the Electronic Data Capture (EDC).
- Retrospective data will be gathered from subjects in Cohort 4: At least three 6MWT results, each at least 6 months apart must be available and entered in the EDC. At least two 6MWT results should be within the past three years. Additionally, pulmonary function tests, other motor function tests such as 10-meter walk, 4-stair climb, and Gower's, quantitative (dynamometry) and qualitative muscle strength tests, GSGC score, and PROs, if available should be recorded in the EDC. In addition to the above requirement, all available data will be collected.

Stage 1, Periods 1, 2, and 3:

- Safety: review of AEs, including SAEs and IARs; review of concomitant medications and nondrug therapies; vital signs (HR, RR, BP, and temperature); brief PE; ECG; clinical safety laboratory assessments (serum chemistry, hematology, and urinalysis); and urine pregnancy test.
- PD: urinary Hex4 and serum CK.
- Immunological: blood samples for anti-rhGAA antibodies (total, neutralizing, and cross-reactive with alglucosidase alfa) and blood samples for measurement of pro-inflammatory cytokines and other biomarkers of immune system activation. If needed, IgE and total GAA protein concentration will also be measured.

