6.4.2.6. ATB200 Preliminary Efficacy Data

The fourth interim analysis was conducted in September 2017 with data cut-off point in August 2017.

Adverse events (AEs) were generally mild and transient. Most common AEs reported as treatment related were nausea (3/20), tremor (3/20), headache (3/20), fatigue (3/20), diarrhea (2/20), muscle spasm (2/20), and joint swelling (2/20). Three incidents of infusion-associated reactions (IARs) in 400⁺ infusions which were controlled by standard premedication. One IAR event occurred in one nonambulatory ERT-switch patient (skin discoloration). Two IAR events in an ERT-naïve patient (localized pruritus, erythema and burning sensation). Longest duration of treatment was 72 weeks.

Improvement in biomarkers of muscle damage (creatine phosphokinase [CK], alanine aminotransferase [ALT], and aspartate aminotransferase [AST]) and disease substrate (hexose tetrasaccharide [Hex4]) was observed for up to 58 Weeks on ATB200/AT2221 in all three cohorts.

Six-minute walk distance improved in Cohorts 1 and 3 as shown in [Table 6](#). Qualitative and quantitative upper extremity muscle strength improved in Cohort 2 subjects. Forced vital capacity was stable in Cohort 1 and improved in Cohort 3 as shown in [Table 7](#).

Table 6: Change in 6MWT Distance in Meters in Cohorts 1 and 3 Subjects Through Month 18

Cohort	Mean (SD)	Mean (SD) Change from Baseline			
	Baseline	Month 6	Month 9	Month 12	Month 18
1^a ERT-experienced (2 to 6 years)	(n = 10) 397.2 (96.8)	(n = 10) +23.9 (52.2)	(n = 10) +24.5 (40.8)	(n = 10) +42.2 (46.5)	(n = 9) +51.7 (45.9)
3 ERT-naïve	(n = 5) 399.5 (83.5)	(n = 5) +41.8 (29.4)	(n = 5) +63.5 (23.1)	(n = 5) +63.1 (29.1)	(n = 5) +49.0 (28.3)

Abbreviations: 6MWT = 6-minute walk test; ERT = enzyme replacement therapy; n = number of patients; SD = standard deviation

^a For the purposes of assigning nominal time points to data from Cohort 1, the 6-week duration of Stage 1 (single ascending doses of miglustat) and the 12-week duration of Stage 2 (multiple ascending doses of miglustat [130 mg for 6 weeks, followed by 260 mg for 6 weeks]) were included. Therefore, the Month 6, 9, 12, and 18 time points reflect cumulative data to Stage 3 Month 3, Stage 3 Month 6, Stage 3 Month 9, and Stage 3 Month 15, respectively.

Source: Interim Analysis 6 (data cut-off date of August 2018), Table 14.2.1.3

Table 7: Change in Percentage Predicted Sitting FVC (%) in Cohorts 1 and 3 Subjects Through Month 18

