18. Male and female subjects between 18 and 65 years of age, inclusive
19. Subject must provide signed informed consent prior to any study-related procedures
20. Subjects of childbearing potential must agree to use medically accepted methods of contraception during the study and for 90 days after last co-administration of ATB200 and AT2221
21. Subject has a diagnosis of Pompe disease based on documented deficiency of GAA enzyme activity or by *GAA* genotyping
22. Subject must be able to walk between 200 to 500 meters on the 6MWT
23. Upright FVC must be 30% to 80% of predicted normal value

Exclusion Criteria

23. Subject has received any ERT, including alglucosidase alfa at any time, or any investigational therapy for Pompe disease within 30 days or 5 half-lives of the therapy or treatment, whichever is longer, prior to the Baseline Visit, or anticipates doing so during the study

24. Subject has received treatment with prohibited medications (see Section 8.7) within 30 days of the Baseline Visit
25. Subject, if female, is pregnant or breastfeeding at screening
26. Subject, whether male or female, is planning to conceive a child during the study
27. Subject requires invasive ventilatory support
28. Subject uses noninvasive ventilatory support \geq 6 hours a day while awake
29. Subject has a medical or any other extenuating condition or circumstance that may, in the opinion of the investigator or the Medical Monitor, pose an undue safety risk to the subject or compromise his/her ability to comply with protocol requirements
30. Subject has a history of allergy or sensitivity to miglustat or other iminosugars
31. Subjects with active systemic autoimmune disease such as lupus, scleroderma, or rheumatoid arthritis; all subjects with autoimmune disease must be discussed with the Amicus Medical Monitor
32. Subjects with active bronchial asthma; all subjects with bronchial asthma must be discussed with the Amicus Medical Monitor

Cohort 4

Inclusion Criteria

24. Male and female subjects between 18 and 75 years of age, inclusive
25. Subject must provide signed informed consent prior to any study-related procedures
26. Subject has documented 6MWT on three separate occasions, each at least six months apart with at least two values in the past three years
27. Subjects of childbearing potential must agree to use medically accepted methods of contraception during the study and for 90 days after last co-administration of ATB200 and AT2221

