6.2. General Methodology and Presentation

6.2.1. General Methodology

There will be no inferential statistics as no hypothesis tests were planned for this study. In general, continuous variables will be summarized using descriptive statistics including the number of subjects (n), mean, standard deviation (SD), median, the first quartile (Q1), third quartile (Q3), minimum, and maximum. Unless otherwise stated, these summaries will be provided for the raw values, absolute change from baseline, and the percent change from baseline values. Where appropriate, a 95% confidence interval (CI) for the mean change from baseline will be provided for summary purposes. Categorical variables will be summarized using frequencies (counts) and percentages.

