10.3.3. Additional Analysis of IARs

10.3.3.1. Analysis by Onset Intervals

The onset intervals (in months), defined relative to the first dose of the 20 mg/kg ATB200 + 260 mg AT2221 study drug, will be: ≤ 6 , > 6 to ≤ 12 , > 12 to ≤ 18 , > 18 to ≤ 24 , and > 24 . For Cohort 1 subjects, the first dose of the 20 mg/kg ATB200 + 260 mg AT2221 study drug happened in Stage 2 Period 5.

The event rates and changes in intensity over time (over these intervals) will be summarized. This analysis will further describe the clinical characteristics of IARs, and it can help determine whether the IARs disappear over time or appear late.

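### The IAR timing tables put nearly all of Stage 4 into one open interval and start Cohort 1's clock at its seventh ATB200 infusion, which blurs late onset and mixes exposure times in pooled columns

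*SAP*

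**What the plan says.** - **Onset intervals (SAP 10.3.3.1).** IAR onset is grouped as up to 6, over 6 to 12, over 12 to 18, over 18 to 24, and over 24 months. Event rates and intensity are summarised over these intervals. The stated use is that "it can help determine whether the IARs disappear over time or appear late".
- **Clock (SAP 10.3.3.1, 10.3.3.2).** Time runs from the first dose of the fixed 20 mg/kg + 260 mg regimen: "For Cohort 1 subjects, the first dose of the 20 mg/kg ATB200 + 260 mg AT2221 study drug happened in Stage 2 Period 5". Time to first IAR uses the same origin, counts only IARs on that regimen, and leaves out subjects with none.
- **Columns (SAP 6.2.2.3).** Safety results from Period 5 onward are shown for each cohort, for pooled ambulatory subjects (Cohorts 1, 3 and 4), and in total.
- **History split (SAP 10.3.2).** "The IAR summary will also be presented by prior history of IARs (yes/no". The protocol synopsis says, for Screening, "For subjects in Cohorts 1, 2, and 4, a history of prior infusion-associated reactions (IARs) will also be obtained", and for Baseline, "Additionally, a history of IARs will be obtained for subjects in Cohorts 1, 2, and 4". Cohort 3 has no earlier ERT by design; its first exclusion criterion begins "Subject has received any ERT, including alglucosidase alfa at any time".

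**The concern.** The interval table is meant to show whether IARs fade or emerge late. If everything after two years is one cell, a cluster in year three and a cluster in year seven look the same. If that cell is read as a raw count, its length alone can make IARs look late.

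The pooled columns have a separate problem. The earliest interval is where first-exposure reactions would show. There, Cohort 1 contributes subjects who have already had six ATB200 infusions, while the other cohorts contribute subjects at their first. Mean time to first IAR carries the same shift: a Cohort 1 subject who reacted during the first six infusions would either be given a later first IAR or not be counted.

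The history split raises a smaller question: where do subjects who never had an ERT infusion go in a yes/no variable about reactions to one?

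**Working it through.** **1. Cohort 1's clock.** Inputs: the visit days in Protocol Table 9 and the Day 85 reference start in SAP 6.4.5. With dosing every 14 days, infusion k falls on day 1 + 14(k − 1). Visits 3 to 8 give k = 1 to 6 on Days 1, 15, 29, 43, 57 and 71. For k = 7, 1 + 14 × 6 = 85, which reproduces the SAP's Visit 9. Six infusions therefore precede the clock: three of ATB200 alone and three with 130 mg AT2221. Over the 11 planned subjects that is 11 × 6 = 66 infusions.

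**2. Size of the shift.** 85 − 1 = 84 days, and 84 / 30.4 = 2.8 months (30.4 days per month, as in SAP 10.2). Cohort 1's first interval covers about months 2.8 to 8.8 after first ATB200; in Cohorts 2 to 4 it covers months 0 to 6.

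**3. Where Stage 4 falls.** The Month 24 target day on the analysis clock is Day 763 in Cohort 1 (SAP Table 4) and Day 721 in the others (Table 5). 763 / 30.4 = 25.1 months and 721 / 30.4 = 23.7 months. Essentially all of Stage 4 is in the open interval, and this step needs no assumed dates.

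**4. Longest possible follow-up.** The documents give no total duration, so it has to be back-calculated. Protocol 6.4.2.6, for a data cut in August 2017 (day not given), says "Longest duration of treatment was 72 weeks". 72 weeks is 504 days. SAP 2 expects database lock on 24 July 2024. Months are (days + 1) / 30.4.

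| Subject | Clock start | Months to lock | After 24 | Share |
|---|---|---|---|---|
| Cohort 1, cut on 31 Aug 2017 | 14 Apr 2016 + 84 d = 7 Jul 2016 | 96.7 | 72.7 | 75% |
| Cohort 1, cut on 1 Aug 2017 | 15 Mar 2016 + 84 d = 7 Jun 2016 | 97.7 | 73.7 | 75% |
| Cohort 4, dosed no earlier than Amendment 5 (16 Feb 2018) | 16 Feb 2018 | 77.3 | 53.3 | 69% |
| Cohort 4, dosed no earlier than Amendment 8 (10 Jan 2019) | 10 Jan 2019 | 66.5 | 42.5 | 64% |

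For the longest-treated Cohort 1 subject the last interval is about 73 / 6 = 12 times as long as each earlier one. It could hold about 158 to 160 of 210 to 212 infusions, against 6 × 30.4 / 14 = 13 per six-month interval. At a constant IAR rate, raw counts for that subject would pile up in the last cell in the same proportion.

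**5. History split.** Planned ERT-experienced subjects number 11 + (4 to 6) + (6 to 8) = 21 to 25; Cohort 3 has 5. *If* Cohort 3 were put under 'no', it would make up 5/30 = 17% to 5/26 = 19% of that group when no experienced subject has a history, and about 29% (5/17) to 33% (5/15) when half do. The actual proportion with a history is not given.

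**The case against.** The case on the other side is substantial.

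- **The origin is a deliberate, disclosed choice.** The SAP uses the fixed-regimen start throughout its long-term safety analysis. The six earlier infusions used other doses or combinations, so timing from the first one would mix regimens in the first interval. This stands: it argues against replacing the origin, though not against a supportive display.
- **Earlier Cohort 1 events are not lost.** They were reported in the first interim report and will be copied into the final one. That stands too, but SAP 6.2.2.3 presents Stages 1 and 2 by dose, not on this timeline.
- **The practical effect on first IARs may be small.** Protocol 6.4.2.6 attributes all three IARs at the August 2017 cut to one nonambulatory and one ERT-naive subject, none to Cohort 1. Table 6 has nine Cohort 1 subjects at Stage 3 Month 15 by August 2018. On target days (577 − 85 = 492 days) they passed Visit 9 by about the end of April 2017. A missed first IAR is therefore possible under the definition but not shown to have happened.
- **Finer timing exists elsewhere.** SAP 10.3.2 lists IARs infusion by infusion for each affected subject, and 10.3 plans AE incidence per patient-year. A reader might infer that late onset cannot be studied at all; that goes too far. However, 10.3.3.1 does not define the denominator of its event rates.
- **Late cells will be sparse.** True, with 26 to 30 planned subjects.

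A reader might also infer that the 'no prior IAR' group contains the ERT-naive subjects. The SAP does not say so: SAP 12.2 has a general missing category, and Cohort 3 has its own column. Nor do three early IARs, two of them in one naive subject, establish confounding by treatment experience. Under 12.2, though, only the number of missing subjects is shown, so Cohort 3's IAR results would drop out of the split.

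**Conclusion.** The point holds for the open interval and for the mixed clock in pooled columns. The open interval takes essentially all of Stage 4. Its share, about 75% for the longest-treated Cohort 1 subject and 64% to 69% of the longest possible Cohort 4 follow-up, is an upper bound: it assumes the 72-week back-calculation or the amendment dates, and dosing up to database lock. Subjects who moved earlier to commercial product or expanded access have less. The figure of about 97 months should not be read as the length of follow-up for every subject. The 2.8-month shift follows from the visit schedule alone and affects only the pooled-ambulatory and Total columns; the separate cohort columns are internally consistent.

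The history split is an undefined level, not a demonstrated misclassification. SAP 6.2.1 states "There will be no inferential statistics as no hypothesis tests were planned for this study", so no test or error rate is affected. The harm is to how the tables are read.

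**What to change.** 1. **SAP 10.3.3.1, intervals.** After 24 months, use 12-month bins to the end of follow-up, and give the IAR rate per patient-year and the number at risk in every bin. The drawback is sparse late cells, which the numbers at risk make visible.
2. **SAP 10.3.3.1 and 10.3.3.2, clock.** Keep the fixed-regimen origin as primary and footnote that for Cohort 1 it is Visit 9, the seventh ATB200 infusion. Add a supportive onset-interval and time-to-first-IAR display timed from the first ATB200 infusion in every cohort.
3. **SAP 10.3.2, infusion counts.** State that infusions and IARs are taken over the same period. The text counts infusions over the study while the events it describes start at Period 5; read literally, up to 66 Cohort 1 infusions could enter the denominator without their IARs.
4. **SAP 10.3.2, history split (minor).** Restrict yes/no to Cohorts 1, 2 and 4 and show Cohort 3 as not applicable (ERT-naive).

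The cost is SAP wording, table shells and some programming before database lock. No new data are needed; SAP 10.3.3.2 says IAR onset dates are already in the database.
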